4 STUDY DESIGN

4.1 Overall design

In this Phase 2, multicenter, randomized, open-label study, the PK, safety, and efficacy of bimekizumab in male and female adolescents (from 12 to <18 years of age) with moderate to severe plaque PSO will be assessed.

The purpose of the study is to evaluate the PK, safety, and efficacy of bimekizumab in adolescent participants and compare the PK and E-R relationship to the adult PSO population. The results will be used to determine the optimal dosing of bimekizumab to be tested in pediatric participants from 6 to <18 years of age with moderate to severe plaque PSO in the Phase 3 efficacy and safety study (PS0021).

The PK, safety, and efficacy of bimekizumab will be evaluated by treating at least 20 participants in each of 2 dose groups (for a total of at least 40 participants evaluable for PK). A participant will be considered evaluable if he/she receives IMP and provides at least 1 sample for PK analysis. Two doses were selected and both are expected to be efficacious based on E-R predictions. Dose A (320mg Q4W in participants ≥ 65 kg and 160mg Q4W in participants < 65 kg) is predicted to provide the same systemic bimekizumab exposure as the 320mg Q4W adult dose, and Dose B (64mg Q4W in participants ≥ 65 kg and 32mg Q4W in participants < 65 kg) is aimed at providing a lower systemic bimekizumab exposure. Weight-categorized dosing during the Initial Treatment Period will be based on the participant's weight at Baseline.

This study will consist of the following periods (as shown in the study schematic in Section 1.2):

- Screening Period: up to 5 weeks
- Initial Treatment Period: 20 weeks (5 doses of bimekizumab; administered sc at Weeks 0 [Baseline], 4, 8, 12, and 16 followed by 4 weeks of observation)
- Open-label Extension Period: 104 weeks (bimekizumab administration starts at Week 20 if participant is eligible, as defined below)
- Safety Follow-up Period: 20 weeks after the final dose of bimekizumab

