5 STUDY POPULATION

Prospective approval of protocol deviations to recruitment and enrollment criteria, also known as protocol waivers or exemptions, is not permitted.

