- Any other laboratory abnormality, which, in the opinion of the Investigator, will prevent the participant from completing the study or will interfere with the interpretation of the study results. Individual screening tests for which the results are in error, borderline, or indeterminate for inclusion in the study can be repeated once for confirmation during the Screening Period. Upon retesting, participants whose results remain outside this threshold should not be randomized.

Prior/Concomitant therapy

17. Participant has previously participated in this study or has received bimekizumab in another study.
18. Participant has received drugs listed in [Table 5-1](#) outside the specified timeframes relative to the Baseline Visit or receives prohibited concomitant treatments (see Section 6.5.2).

Table 5-1: Exclusions for prior treatments

Drug class	Dose	Washout period relative to Baseline Visit
Systemic retinoids	Any dose	4 weeks
Systemic treatment (non-biological) Systemic immunosuppressant agents (eg, methotrexate, cyclosporine, azathioprine, thioguanine) Systemic fumarate/fumaric esters specifically used for treatment of PSO Systemic corticosteroids Photo/chemotherapy	Any dose	4 weeks
Anti-TNFs Adalimumab Infliximab, golimumab, certolizumab pegol (including biosimilars for any of these anti-TNFs) Etanercept (including biosimilar)	Any dose	12 weeks for infliximab, golimumab, adalimumab, certolizumab pegol 4 weeks for etanercept

Table 5-1: Exclusions for prior treatments

Drug class	Dose	Washout period relative to Baseline Visit
Other biologics and other systemic therapies: Ustekinumab Briakinumab Apremilast, tofacitinib Alefacept, efalizumab, guselkumab Rituximab	Any dose	24 weeks for ustekinumab and briakinumab 2 weeks for apremilast/tofacitinib 12 weeks for alefacept, efalizumab, and guselkumab 52 weeks for rituximab
Anti-IL-17 therapy (including ixekizumab and secukinumab)	Any dose	12 weeks (any prior use of bimekizumab is excluded)
Any other antipsoriatic agent (systemic) under investigation (or approved after the protocol is approved)	Any dose	12 weeks (or 5 half-lives, whichever is longer)
Topical agents (except as outlined in Section 6.5.1) Topical corticosteroids for dermatological use Vitamin D analogs, topical retinoids, and topical calcineurin inhibitors Keratolytics and coal tar	Any dose	2 weeks
Any other topical antipsoriatic agent under investigation	Any dose	4 weeks

IL=interleukin; PSO=psoriasis; TNF=tumor necrosis factor

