6.5.2 Prohibited concomitant treatments (medications and therapies)

For prohibited prior medications, refer to the exclusion criteria (Section 5.2).

The following concomitant medications and therapies are prohibited during the study:

- Systemic agents:
 - Systemic retinoids
 - Systemic immunosuppressant agents (eg, methotrexate, cyclosporine, azathioprine, thioguanine)
 - Systemic fumarate
 - Systemic corticosteroids
 - Any other antipsoriatic agent (systemic) under investigation (or approved after the protocol is approved)
- Photo/chemotherapy
- Biologic therapies (other than bimekizumab)
- Topical agents for dermatologic use:

- High potency topical corticosteroids (Class I, II, and III)
- Any other antipsoriatic agent (topical) under investigation
- Mild (Class VII) to moderate (Class IV) potency topical corticosteroids before Week 20
- Keratolytics and coal tar for PSO before Week 20
- Vitamin D analogs, topical calcineurin inhibitors, and topical retinoids for PSO before Week 20

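### Table 5-1 sets no washout for a non-IL-17 biologic that was already approved at protocol approval and is not named in the table

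*Protocol*

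**What the plan says.** Criterion 18 in Protocol Section 5.2 begins "Participant has received drugs listed in" Table 5-1 and excludes candidates who fall outside the table's timeframes. Its second limb excludes anyone who currently receives a treatment prohibited by Section 6.5.2.

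Table 5-1 ties its anti-TNF and other-biologics washouts to named drugs, for example "12 weeks for infliximab, golimumab, adalimumab, certolizumab pegol" and "12 weeks for alefacept, efalizumab, and guselkumab". The anti-IL-17 row is worded as an open class. The systemic catch-all row covers "Any other antipsoriatic agent (systemic) under investigation (or approved after the protocol is approved", with a washout of "12 weeks (or 5 half-lives, whichever is longer".

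Section 6.5.2 bans every biologic other than bimekizumab during the study. For earlier treatment it adds nothing of its own: "For prohibited prior medications, refer to the exclusion criteria (Section 5.2".

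Section 5 rules out case-by-case exceptions: "Prospective approval of protocol deviations to recruitment and enrollment criteria, also known as protocol waivers or exemptions, is not permitted".

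**The concern.** The protocol treats every biologic as incompatible with bimekizumab on study, and asks for a look-back for each biologic it names and for each investigational or later-approved systemic agent. One category gets no look-back: a biologic outside the IL-17 class, already on the market when the protocol was approved, and not named. No reason is given for that difference. Because waivers are barred, eligibility follows the text as written.

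What is at stake is mainly the reading of early safety data. Section 2.3 bases the safety topics of interest partly on risks common to biologic immunomodulators, and infections are among those topics. Under Section 9.4.1.1, treatment-emergent events count from the first bimekizumab dose, so an infection to which an earlier biologic contributed would be reported under a bimekizumab dose group. With about 20 participants per dose group, one participant is 1/20 = 5 percentage points.

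**Working it through.** There is no planned figure to reproduce. The check takes the drug in question (a biologic, not anti-IL-17, approved before protocol approval, not named) through each row of Table 5-1, and then through the other text that might supply a washout.

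| Table 5-1 row | Washout | Does it reach the drug? |
|---|---|---|
| Systemic retinoids | 4 weeks | No |
| Non-biological systemic agents, photo/chemotherapy | 4 weeks | No; limited to non-biological treatment |
| Anti-TNFs | 12 weeks, or 4 for etanercept | Only five named agents and biosimilars |
| Other biologics and systemic therapies | 2, 12, 24 or 52 weeks | No; each period is attached to named drugs |
| Anti-IL-17 | 12 weeks | No, by definition; unnamed IL-17 agents are covered |
| Systemic catch-all | 12 weeks or 5 half-lives | No; not under investigation and not approved later |
| Topical rows | 2 or 4 weeks | No |

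Result: no row applies.

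Other possible sources of a washout:

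- **Criterion 18, second limb.** It catches someone who is receiving a prohibited treatment, but not someone who has stopped.
- **Criterion 19.** It concerns primary failure of earlier biologics, not time since the last dose.
- **Criterion 22.** It sets 3 months or 5 half-lives, but only after participation in another study. A biologic prescribed in routine care is outside it.
- **Section 6.5.2.** It refers earlier treatment back to Section 5.2.

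Result: no other text supplies a look-back.

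For comparison, Table 5-1 names 13 biologics:

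- 12 weeks, 9 drugs: infliximab, golimumab, adalimumab, certolizumab pegol, alefacept, efalizumab, guselkumab, ixekizumab, secukinumab
- 24 weeks, 2 drugs: ustekinumab, briakinumab
- 52 weeks, 1 drug: rituximab
- 4 weeks, 1 drug: etanercept

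So 9/13 = 69% carry 12 weeks, and none carries less than 4.

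The shortest interval the text enforces for the unnamed drug comes indirectly. Section 10.1.3 counts a participant as enrolled once consent is signed, so the Section 6.5.2 ban is reasonably read as starting then. Section 4.1 gives "Screening Period: up to 5 weeks", or 5 × 7 = 35 days, and footnote m of Table 1-1 requires Screening to finish at least 10 days before Baseline. A last dose just before consent therefore falls about 10 to 35 days before the first bimekizumab dose. Against the usual 12 weeks (12 × 7 = 84 days), that is 84 − 35 = 49 to 84 − 10 = 74 days shorter.

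**The case against.** The strongest objection is that the gap may be empty. The documents identify no drug that fits it and no participant who took one, and naming a product would need approval dates from outside. That stands, and it limits the point to a weakness in the eligibility rule.

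The wording also leaves some room. The other-biologics heading sits in a column for drug classes and could be read as a class, but an unnamed member would still have no period assigned. The phrase about agents under investigation could be stretched to an adult-approved drug still being studied in adolescents, but the bracket on later approvals points the other way. It is unclear whether protocol approval means the original or an amendment; that moves the cut-off date without closing the gap.

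Other controls reduce the risk. A patient on continuing maintenance treatment is arguably caught by the second limb of criterion 18. Infection, tuberculosis and blood counts are screened, and a DMC reviews safety. A 35-day interval is also longer than the 4 weeks accepted for etanercept. These points lower the stakes but do not supply a look-back.

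Three stronger readings are tempting, and the documents do not support them:

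- **A multiple of residual drug compared with the named biologics.** This would rest wholly on assumed half-lives. The documents give none, either for the unnamed drug or for the named ones.
- **Material carry-over into PASI or IGA response.** Section 5.1 requires BSA of at least 10%, IGA of at least 3, and PASI of at least 12 (or 10 with special-site involvement), and Table 1-1 checks eligibility again at Baseline. Carry-over should be uncommon.
- **Distortion of the primary PK endpoint.** Nothing in the documents shows that an earlier biologic would change bimekizumab concentrations.

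**Conclusion.** The gap is real as a matter of text. A candidate who stopped an already approved, unnamed, non-IL-17 biologic just before consent is eligible, whereas every named biologic needs 4 to 52 weeks. The number affected is unknown and may be zero. The consequence is mainly possible overlapping immunomodulation in early safety data, and its size cannot be estimated from the documents. The conclusion rests on reading the named lists as closed and the catch-all row as excluding earlier approvals. The 10-to-35-day interval also assumes that the on-study ban starts at consent. A reader might infer that participants were in fact enrolled with another biologic on board; nothing in the documents shows this. This is a low-cost improvement to the eligibility rule, not a flaw that undermines the study.

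**What to change.** Add one row to Table 5-1 for any other biologic therapy not listed above, with the catch-all row's existing value: "12 weeks (or 5 half-lives, whichever is longer". This matches the breadth of the biologic ban in Section 6.5.2. Leave the non-biological entries unchanged, including the 2 weeks for apremilast and tofacitinib. The value is stricter than the flat 12 weeks given to 9 of the 13 named biologics, but it is the one the table already applies to systemic agents it does not name. The cost is that a few candidates wait or are rescreened; Section 5.4 already lists an unmet washout as a reason for rescreening.

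SAP version 3.0 gives database lock as part of its rationale, so for this study the row helps only if the table is reused. The remaining action is to list anyone who had such a biologic within that window before Baseline, from the prior-medication and past-psoriasis-treatment data (SAP Sections 6.1.4 and 6.1.5). SAP Section 5.1 already plans full data listings, but the described summary of prior biologics (SAP Section 6.1.1.3) is yes/no with discontinuation reasons and would not show time since last dose. The check works only as far as last-dose dates were recorded, which the SAP does not state for past psoriasis treatments. If nobody falls in the window, one sentence in the study report closes the matter.

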5.3 Lifestyle restrictions

No lifestyle restrictions are required.

5.4 Screen failures

Screen failures are defined as participants who consent/assent to participate in the clinical study but are not subsequently randomized to IMP. A minimal set of screen failure information is required to ensure transparent reporting of screen failure participants to meet the Consolidated Standards of Reporting Trials publishing requirements and to respond to queries from regulatory authorities. Minimal information includes demography, screen failure details, eligibility criteria, and any serious adverse event (SAE).

Individuals who do not meet the criteria for participation in this study (screen failure) may be rescreened once after consultation with the Medical Monitor. Rescreened participants should be assigned a new participant number. Reasons for rescreening include, but are not limited to, the following:

- Study participant needs to complete 8 weeks of prophylaxis for LTBI prior to rescreening described in the exclusion criteria (Section 5.2).
- Individual laboratory screening tests for which the results are exclusionary can be retested. For example, tests that result in ALT, AST, or ALP up to 25% above the exclusion limit may be repeated once for confirmation; however, the Investigator will need to discuss with the Medical Monitor to help understand the elevation before the participant can be enrolled. Test can also be repeated during rescreening. Repetition of laboratory screening tests within the Screening Period for other than technical reasons (eg, frozen sample, expired laboratory kit) may not be performed without approval by Medical Monitor.
- Eligibility assessments could not be completed as planned (eg, for technical reasons) within the defined Screening Period of 5 weeks without approval by Medical Monitor.
- Participant does not meet the required washout period for concomitant medications.

6 STUDY TREATMENTS

Study treatment is defined as any investigational treatment(s), marketed product(s), placebo, or medical device(s) intended to be administered to a study participant according to the study protocol.

6.1 Treatments administered

ARM Name	Dose A	Dose B
Intervention name	Bimekizumab	Bimekizumab
Type	Biologic	Biologic
Dose presentation	██████████ ██████████	██████████ ██████████
Unit dose strength(s)	160mg/mL	160mg/mL
Dosage level(s) ^a	Dose A, administered Q4W, will be based on weight at Baseline 320mg in participants ≥65kg and 160mg in participants <65kg	Dose B, administered Q4W, will be based on weight at Baseline 64mg in participants ≥65kg and 32mg in participants <65kg
Dose administration performed by	Health care professional, caregiver (once training is received), or study participant (once he/she becomes 18 years of age and training is received)	Health care professional (in order to ensure accuracy as this dose is drawn up from a vial)
Route of administration	sc injection	sc injection
Use	Open-label	Open-label
IMP and NIMP	IMP	IMP
Sourcing	Provided centrally by the Sponsor	Provided centrally by the Sponsor
Packaging and labeling	Study intervention will be provided in PFS. Each PFS will be labeled as required per country requirement.	Study intervention will be provided in vials. Each vial will be labeled as required per country requirement.

IMP=investigational medicinal product; NIMP=non-investigational medicinal product; OLE=Open-label Extension; PFS=prefilled syringe; Q4W=every 4 weeks; sc=subcutaneous

NOTE: For both Dose A and Dose B, IMP administration is to occur at the site in the Initial Treatment Period and may occur at home or at the site in the OLE Period.

^a Dose modifications are allowed, as described in Section 6.6.

6.2 Preparation, handling, storage, and accountability requirements

For the first 5 doses of IMP (during the Initial Treatment Period), a health care professional at the study site will be responsible for preparation of the clinical study material, including recording the administration information on source documents and administration of the IMP as sc injections. In the OLE Period, Dose A and Dose B may be administered at the study site or

where possible at home. Home visits can be conducted during the OLE Period upon agreement of the Investigator, study participant, and his/her caregiver. Dose A of the IMP may be administered by a health care professional, his/her caregiver, or study participant (once he/she becomes 18 years of age). Dose B will be administered by a health care professional, to ensure accurate dosing of the lower volume of IMP (Table 1-1 and Table 1-2). Training to administer Dose A of the IMP will be provided by qualified study personnel at least 2 visits prior to the first visit at which IMP is planned to be administered by the caregiver or study participant (once he/she becomes 18 years of age). During the next visit, the caregiver/study participant will perform administration under the supervision of a health care professional to ensure that IMP is being properly and safely injected.

Once study participants/caregivers are determined by the Investigator (or designee) to be trained, they will receive the required number of syringes to perform administration of Dose A where possible at home. Study participants who are unable or unwilling to self-administer (once he/she becomes 18 years of age) or who do not have a caregiver to administer IMP may have IMP administered by a health care professional at the site or where possible at home. In the case of home administration, dates, body locations, kit numbers, and time of administration will be documented.

Suitable areas for sc injections are the lateral abdominal wall, upper outer thigh, or upper arm. During each dosing visit, each of the injections should be administered at a separate injection site. Injection sites should be rotated at each visit and injections should not be given into a PSO plaque or areas where the skin is tender, bruised, erythematous, or indurated. The injection should last approximately 10 to 15 seconds.

An IMP Handling Manual will be provided to each site containing instructions regarding drug preparation and dosing.

Only participants enrolled in the study may receive IMP and only authorized site staff/health care professional may supply IMP. All IMP must be stored in a secure, environmentally controlled, and monitored (manual or automated) area in accordance with the labeled storage conditions, with access limited to the Investigator and authorized site staff.

In addition, the Investigator (or designee) will instruct the health care professional, caregiver, or study participant on how to handle the IMP during transport and how to store the IMP following the instruction guide. Cooler bags with freezer packs will be provided. Additional information will be provided in the IMP Handling Manual.

The Investigator, institution, or the head of the medical institution (where applicable) is responsible for IMP accountability, reconciliation, and record maintenance (ie, receipt, reconciliation, and final disposition records).

In case an out-of-range temperature is noted, it must be immediately reported as per instructions contained in the IMP Handling Manual.

Further guidance and information for the final disposition of unused IMP are provided in the IMP Handling Manual.

6.2.1 Drug accountability

The Drug Accountability Form will be used to record IMP dispensing and return information on a by-participant basis and will serve as source documentation during the course of the study.

Details of any IMP lost, damaged (due to breakage or wastage), not used, partially used, disposed of at the study site, or returned to the Sponsor or designee must also be recorded on the appropriate forms. All supplies and pharmacy documentation must be made available throughout the study for UCB (or designee) to review.

The date, body location, kit number, and time of administration of IMP will be documented. All used syringes (Dose A and B) and vials (Dose B only) will be disposed of by the health care professional, caregiver, or study participant in a disposal (sharps) container directly after the administration. The Investigator (or designee) is responsible for retaining all used, unused, and partially used containers of IMP until returned or destroyed.

The Investigator may assign some of the Investigator's duties for drug accountability at the study site to an appropriate pharmacist/designee.

The Investigator must ensure that the IMP is used only in accordance with the protocol.

Periodically, and/or after completion of the clinical phase of the study, all used (including empty containers)/partially used, unused, damaged, and/or expired IMP must be reconciled and either destroyed at the site according to local laws, regulations, and UCB Standard Operating Procedures or returned to UCB (or designee). Investigational medicinal product intended for the study cannot be used for any other purpose than that described in this protocol.

6.3 Measures to minimize bias: Randomization and blinding

This is an open-label study; however, the specific intervention to be taken by a participant will be randomly assigned using an interactive voice response system (IVRS)/interactive web response system (IWRS). The site will contact the IVRS/IWRS prior to the start of IMP administration for each participant. The site will record the intervention assignment on the applicable eCRF, if required. Participant randomization will be produced by the IVRS/IWRS vendor. The randomization will be stratified by weight category.

Investigational medicinal product will be dispensed at the study visits summarized in the Schedule of Activities ([Table 1-1](#) and [Table 1-2](#)).

Returned IMP should not be re-dispensed to the participants.

